US patients who sign the informed consent form will be asked to sign a medical billing release form to allow the release of financial information relating to the cost of any trial-related procedures and hospitalizations that occur during their participation in the SAFE-2 trial. This information will be collected for use outside of this IDE study in a future health economics study. Refusal to release medical billing information will have no impact on participation in the IDE.

Screening/Preliminary Eligibility Determination

During screening, if all inclusion criteria and no preoperative exclusion criteria are met, the subject will be considered for enrollment in the study. Note that the intraoperative exclusion criteria cannot be evaluated until the colon resection procedure (index surgery) is complete. At that time, a final determination of eligibility will be made.

Preoperative Assessments

The following preoperative assessments will be performed prior to the index surgery

- Medical history and physical examination to record demographics, tumor characteristics and related treatment
- Quality of Life scores

EQ-5D-5L: The EQ-5D-5L comprises the following five dimensions: Mobility, Self-Care, Usual Activities, Pain/Discomfort and Anxiety/Depression. Each dimension has five response levels: no problems, slight problems, moderate problems, severe problems, unable to/extreme problems. Additionally, the EQ VAS records the respondent's overall current health on a visual analogue scale where the endpoints are labelled "The best health you can imagine" and "The worst health you can imagine."

LARS Score – Low anterior colon resection is associated with bowel dysfunction, which negatively affects the patient's quality of life (QOL). Low Anterior Resection Syndrome (LARS) is characterized by high frequency of bowel movements, clustering, incomplete evacuation, diarrhea, incontinence for flatus and stool, urgency, and bowel movements at night. The severity of LARS can be measured with LARS score, a five-item instrument that consists of frequent bowel movements, gas incontinence, fecal incontinence, fragmentation, and urgency. The LARS score ranges from 0-42, where 0 is no symptoms and 42 is all symptoms at least once per week.

Low Anterior Resection Surgery:

The Low Anterior Resection surgery and creation of the anastomosis will be performed as per standard of care.

Final Eligibility per Intraoperative Exclusion Criteria:

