Day 9 only: EQ-5D-5L and LARs Score quality of life questionnaires will be completed by the subject

EQ-5D-5L Quality of Life (QOL): This questionnaire comprises the following five dimensions: Mobility, Self-Care, Usual Activities, Pain/Discomfort and Anxiety/Depression. Each dimension has five response levels: no problems, slight problems, moderate problems, severe problems, unable to/extreme problems. Additionally, the EQ VAS records the respondent's overall current health on a visual analogue scale where the endpoints are labelled "The best health you can imagine" and "The worst health you can imagine". The total score for the EQ-5D-5L ranges from 5-15, where a high score represents more severe or frequent problems. Low Anterior Resection Syndrome (LARS) Score QOL: This questionnaire consists of five items that include: frequent bowel movements, gas, and fecal incontinence, fragmentation, and urgency. The LARS score ranges from 0-42, where 0 is no symptoms and 42 is all symptoms at least once per week.

Any AEs that have occurred since the previous daily monitoring will be recorded on the AE eCRF.

Day 9 – CT Scan: A double (rectal and IV) contrast CT Scan with 1mm thick slices for acquisition and 2 mm thick slices for reconstruction will be performed at Day 9 (+3 days). Images will be recorded and analyzed to determine the presence or absence of leak and the description of the leak (if applicable). Information will be reported in the eCRF. Any AEs that occur during the procedure will be recorded on the AE eCRF.

Day 10 – Colovac Device Retrieval:

The following steps will be performed for all subjects at Day 10 (-1/+2 days) Note that these procedures may be performed: in the endoscopy unit if anastomosis is healed or in the operating room if the anastomosis is not healed completely, based on the findings of the CT scan performed on Day 9.

If the CT scan described above at Day 9 (+3 days) has not been performed prior to the day of retrieval, perform it before retrieving the Colovac Device.

The Colovac Device will be retrieved according to the Instructions for Use.

Note: An endoscopic examination will be performed *before* the device retrieval to confirm diversion of fecal stream from the anastomosis using the Boston Bowel Preparation Scale (BBPS) score (BBPS = 3). A still image of the circumference of the anastomosis should be obtained and provided to the Sponsor.

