LARS quality of life

EQ-5D-5L quality of life

Testing will continue only if all previously tested null hypotheses of no difference have been rejected at the 2-sided alpha=0.05 significance level in favor of the Colovac treatment.

Hypotheses and associated tests for the secondary effectiveness endpoints are shown in Table 10.

Table 10: Planned Sequence of Key Secondary Effectiveness Tests

Target Claim	Statistical Hypotheses	Statistical Test

The mean cumulative length of hospital stay is significantly less for Colovac subjects through 12 months than the mean cumulative length of hospital stay for Control subjects through 12 months.
	$H_0: \pi_I = \pi_C$ $H_a: \pi_I < \pi_C$ Where, π_I = The mean cumulative length of hospital stay for Colovac subjects through 12 months π_C = mean cumulative length of hospital stay for Control subjects through 12 months	T-test

The mean CCI for Colovac subjects through 12 months is significantly less than the mean CCI for Control subjects through 12 months.
	$H_0: \pi_I = \pi_C$ $H_a: \pi_I < \pi_C$ Where, π_I = The CCI for Colovac subjects through 12 months	T-test

Target Claim	Statistical Hypotheses	Statistical Test
	π_c = The CCI for Control subjects through 12 months	
The mean LARS QOL for Colovac subjects at 6 months is significantly higher than the mean LARS QOL for Control subjects at 6 months.	$H_0: \pi_i = \pi_c$ $H_a: \pi_i > \pi_c$ Where, π_i = The mean LARS QOL for Colovac subjects at 6 months π_c = The mean LARS QOL for Control subjects at 6 months	T-test
The mean ED-5Q-5L QOL for Colovac subjects at 1 month is significantly higher than the mean ED-5Q-5L QOL for Control subjects at 1 month.	$H_0: \pi_i = \pi_c$ $H_a: \pi_i > \pi_c$ Where, π_i = The mean ED-5Q-5L QOL for Colovac subjects at 1 month π_c = The mean ED-5Q-5L QOL for Control subjects at 1 month	T-test

SECONDARY EFFECTIVENESS ENDPOINTS

Secondary Effectiveness Endpoints Comparing the Colovac and Standard of Care Arms

Cumulative Length of Hospital Stay through 12 Months post-discharge: Total length of hospital stay (in days) through the 12-month visit will be compared between the two study arms. As skewed data distributions are expected, an appropriate non-parametric method such as the Wilcoxon's rank sum test or the logrank test (should there be censored data) will be used for analysis.

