Comprehensive Classification Index (CCI): The CCI is the sum of all AEs, weighted by their severity. The CCI will be collected and compared between the treatment group and the control group. The CCI includes all postoperative complications and thus, is more comprehensive and more sensitive than other safety endpoints. The CCI is calculated on the basis of tabulated complications classified according to

the Clavien-Dindo classification. The CCI will be summarized and compared between the two arms as continuous measures.

LARS Quality of Life: The Low Anterior Resection Syndrome (LARS) QOL at 6 months post-index surgery will be compared between study arms using the LARS questionnaire. The questionnaire consists of five items that include: frequent bowel movements, gas, and fecal incontinence, fragmentation, and urgency. The LARS score ranges from 0-42, where 0 is no symptoms and 42 is all symptoms at least once per week. The LARS score at 6 months post-index surgery will be compared between the two treatment arms as a continuous measure. Note that as the LARS questionnaire cannot be completed by subjects in the Control arm until after ostomy reversal, if a Control subject does not have a score at 6 months, the score at the next closest time point will be used. The mean, median, minimum and maximum will be descriptively presented for each arm.

EQ-5D-5L Quality of Life (QOL): Patient QOL at 1 month post-index surgery will be compared between study arms using EQ-5D-5L questionnaire. The EQ-5D-5L comprises the following five dimensions: Mobility, Self-Care, Usual Activities, Pain/Discomfort and Anxiety/Depression. Each dimension has five response levels: no problems, slight problems, moderate problems, severe problems, unable to/extreme problems. Additionally, the EQ Visual Analogue Scale VAS records the respondent's overall current health on a visual analogue scale where the endpoints are labelled 'The best health you can imagine' and 'The worst health you can imagine'. The 5-15 total score for the EQ-5D-5L descriptive dimensions will be summarized as ordinal data for the two treatment arms and compared by Cochran-Mantel-Haenszel test for ordinal data. The VAS score will be summarized and compared between the two arms as continuous measures.

Sigmoidoscopic assessment of anastomosis: The anastomosis will be assessed at 6 and 12-months post-surgery.

Secondary Effectiveness Endpoints for Colovac Arm Only

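### Table 10 states the LARS claim and alternative hypothesis in the direction of harm, against its own gate rule; three smaller gaps sit in the same test sequence

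*Combined protocol and SAP*

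**What the plan says.** Section 8.6.1 tests four secondary endpoints in a fixed order: hospital stay, CCI, LARS, EQ-5D-5L. Each test opens only if all earlier null hypotheses "have been rejected at the 2-sided alpha=0.05 significance level in favor of the Colovac treatment".

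- **LARS.** Table 10 gives the target claim as "The mean LARS QOL for Colovac subjects at 6 months is significantly higher than the mean LARS QOL for Control subjects at 6 months", with Ha: π_I > π_C and a t-test. The LARS text in the same section reads: "The LARS score ranges from 0-42, where 0 is no symptoms and 42 is all symptoms at least once per week". The secondary endpoint definition, the preoperative assessments and the Day 9 questionnaires give the same range and anchors, and the preoperative assessments add: "The severity of LARS can be measured with LARS score".
- **EQ-5D-5L.** Table 10: "The mean ED-5Q-5L QOL for Colovac subjects at 1 month is significantly higher than the mean ED-5Q-5L QOL for Control subjects at 1 month", with a t-test. The text of 8.6.1 has two scores: a total, "compared by Cochran-Mantel-Haenszel test for ordinal data", and a VAS compared as a continuous measure. The Day 9 section states: "The total score for the EQ-5D-5L ranges from 5-15, where a high score represents more severe or frequent problems".
- **Hospital stay.** Table 10 lists a t-test. The text says that "an appropriate non-parametric method such as the Wilcoxon's rank sum test or the logrank test (should there be censored data) will be used".
- **LARS timing.** If a Control subject has no 6-month score, the nearest other time point is used (secondary endpoint definition and 8.6.1). The Table 6 footnote and the Colovac follow-up section say that converted Colovac subjects complete LARS only after reversal. Section 8.5.2 allows no imputation for efficacy analyses other than the primary.

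**The concern.** The LARS claim and Ha say that Colovac should score higher on a scale where higher is worse. A rejection in the printed direction would show more bowel dysfunction with Colovac, yet the gate opens only on a result favourable to Colovac. One result cannot satisfy both. LARS is a multiplicity-controlled test and stands before EQ-5D-5L, so if the conflict remains at unblinding, the sponsor would have to choose between the two statements with the data in view.

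The lesser gaps leave similar choices open: which EQ-5D-5L score and test count, which hospital-stay p-value opens the first gate, and what happens to a converted Colovac subject who has no 6-month LARS score.

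**Working it through.** The plan gives no effect size, standard deviation or power for LARS or EQ-5D-5L, so it has no figure of its own to reproduce on this point. The main check sets the texts side by side.

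**1. Direction of each row of Table 10**

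| Endpoint | Better score per the plan | Ha in Table 10 | Consistent? |
|---|---|---|---|
| Hospital stay | lower | π_I < π_C | yes |
| CCI (severity-weighted sum of AEs) | lower | π_I < π_C | yes |
| LARS (0 none, 42 worst) | lower | π_I > π_C | no |
| EQ-5D-5L | total: lower; VAS: numeric direction not stated | π_I > π_C | not for the total; for the VAS only if higher is better |

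For LARS the words and the symbol agree with each other, so this is not a lost character. No section reverses or rescales the score. The sponsor's list of potential benefits expects quicker recovery of digestive function and better quality of life, that is, lower LARS.

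**2. EQ-5D-5L score**

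A high total is worse and the total is assigned Cochran-Mantel-Haenszel, so *higher* with a t-test can fit only the VAS. The t-test is weak evidence of intent, because Table 10 also lists one for hospital stay against its own text. Range of the total, if levels are coded 1 to 5: 5 × 1 = 5 to 5 × 5 = 25. The stated maximum of 15 equals 5 × 3, which would fit three levels; the plan describes five.

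**3. Converted Colovac subjects and the LARS rule**

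Inputs: 171 per arm, 7% loss and about 70% avoidance (section 8.4). The share q of stomas reversed by 6 months is not given and is assumed.

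- Followed per arm: 171 × 0.93 = 159.
- Converted: 159 × 0.30 = 48.
- Converted with no 6-month score: 48 × (1 − q).
  - q = 0: 48 (30% of 159), the upper bound.
  - q = 0.5: 24 (15%).
  - q = 0.8: 10 (6%).

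At the 50% avoidance used as the planning threshold, 159 × 0.50 = 80 are converted, and the same q values give 80, 40 and 16.

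The introduction says that reversal is usually deferred for up to 6 months and that about 20% of stomas are never reversed. If 20% applies to both arms, a rule covering both arms would recover 48 × (0.80 − q): 14 at q = 0.5 and 0 at q = 0.8. For comparison, the Control rule keeps up to 159 × 0.80 = 127; without it Control would have 159 × q, that is 80 at q = 0.5 and 127 at q = 0.8. The 6-month visit window of ±30 days lowers the affected counts further, since a reversal shortly after month 6 can still yield a 6-month score.

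**The case against.** The strongest reply is that the operative rule is right. H0 is equality, the test is two-sided at 0.05, and the gate needs a rejection favourable to Colovac. An analyst who follows the gate would test LARS correctly and open EQ-5D-5L correctly. This stands. It limits the consequence but leaves the prespecified claim and Ha wrong.

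A reader might infer that the LARS test cannot succeed as planned. With 159 per arm and assumed benefits of 0.2 to 0.5 SD, the chance of rejecting in the printed direction is close to zero, against 43% to 99% in the corrected direction. That contrast treats Ha as a one-sided rule and uses effect sizes that are not in the documents. The two-sided gate wording does not support it.

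A reader might also infer that converted Colovac subjects are dropped from the LARS comparison, and that this favours Colovac. The plan is silent on them. Leaving them out follows only if the Control-only rule is read together with the no-imputation sentence, and that sentence does not clearly govern substitution of visits, since the Control substitution coexists with it. The introduction's reversal figures, taken together, also point nearer to q = 0.8 than to q = 0, and at q = 0.8 the both-arm rule recovers nobody. Nothing in the documents fixes the direction of any bias.

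**Conclusion.** The LARS target claim and Ha in Table 10 are wrong as written and should be corrected. This rests on the plan's own scale definition, given in four places, and on the gate rule. The p-value does not change, the intended direction is clear, and the error is confined to the third gated secondary test. LARS is reached only if hospital stay and CCI both succeed. The co-primary endpoints are unaffected.

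The lesser points hold in limited form. The gated EQ-5D-5L score is unnamed, and the stated range of the total does not fit five levels coded 1 to 5. The first gate has a separate conflict, t-test in the table against a non-parametric method in the text. No LARS substitution rule is stated for converted Colovac subjects: about 48 of 159 is the upper bound at 70% avoidance, and about 24 or 10 at the assumed 50% or 80% reversed, fewer with the visit window. No net bias is claimed.

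**What to change.** Before any unblinded comparison of the arms:

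1. In Table 10, change the LARS claim to *significantly lower*, with Ha: π_I < π_C.
2. Name the one EQ-5D-5L score tested in the gate, with its matching test and direction: the total with Cochran-Mantel-Haenszel and *lower*, or the VAS with *higher* and a statement that a higher VAS is better. Correct the range of the total to 5–25, in the Day 9 section and in 8.6.1, if levels are coded 1 to 5.
3. Make the hospital-stay test in Table 10 match the non-parametric method in the text of 8.6.1.
4. In the LARS endpoint definition and in 8.6.1, apply one rule to any subject in either arm who lacks a 6-month LARS score: use the follow-up score closest to month 6 that was taken with no stoma in place, never a preoperative or Day 9 score. Report by arm how many have none. The rule should not be limited to subjects with a stoma at 6 months, because the present text also covers a Control subject who lacks a 6-month score for another reason. The Day 9 exclusion is needed because Colovac subjects complete LARS on that day.

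Cost: wording only, with no new visits or data. Converted Colovac subjects would enter the LARS comparison, which may make it less favourable to Colovac. Differences in time since bowel continuity was restored would remain.

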Secondary Objectives	
The secondary objectives of the investigation are:
 
 To compare the cumulative length of hospital stay within 12 months post-discharge To provide an additional assessment of product safety via the Comprehensive Classification Index (CCI) To evaluate patient quality of life via the LARS Score within 12 Months To evaluate patient quality of life via the EQ-5D-5L Quality of Life within 12 Months To assess the performance of the Colovac device in diversion of fecal stream, avoidance of clinically significant and symptomatic AL, and avoidance of clinically significant migration To evaluate diversion of fecal stream assessed by endoscopic evaluation before device removal To evaluate the absence of clinically significant and symptomatic leak. To evaluate avoidance of clinically significant migration To evaluate the mucosal appearance (integrity of the anchoring site) and the integrity of the anastomosis after the device retrieval To evaluate the integrity of the anchoring site at 6 and 12 months To assess the patient acceptance and tolerability of the device, during the Colovac Device implantation period
Secondary Effectiveness Endpoints	
The secondary endpoints are:
 
For Comparison between the Colovac and Control Arms:
 
 Cumulative length of hospital stay during the 12 months post-discharge Comprehensive Classification Index (CCI) Patient Quality of Life: LARS Patient Quality of Life: EQ-5D-5L

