Colorectal cancer is the third most common malignancy worldwide and the second most common in the US¹. It is the second leading cause of cancer death worldwide, with 1.8 million new cases and 862,000 deaths per year². The majority of patients receive surgical treatment³. Colorectal surgery is associated with a high risk of morbidity and mortality in comparison to other general surgery subspecialties. Overall mortality rates following colorectal surgery range from 1 to 16.4%, with morbidity rates as high as 35%⁴. Postoperative complications occur in up to 43% of patients undergoing colorectal procedures⁵. Major postoperative complications include surgical site infection, ileus, bleeding and anastomotic complications.

The most serious complication of this surgery is anastomotic leakage, defined as a communication between the intra- and extraluminal compartments owing to a defect in the integrity of the intestinal wall at the level of the anastomosis. This can result in the rapid development of severe peritonitis, septic shock, and multi-organ dysfunction, and can increase the mortality risk.

Known risks for anastomotic leakage include distance of anastomosis location from the anal verge and decreased perfusion of the proximal colon/conduit⁶. The anastomosis itself presents a risk of leak, stricture, and fistula. The anastomotic leak rate is especially high after low anterior resection of rectum, about 10-30%, even when protected with a diverting ostomy²¹. Many of these are major complications that are more severe, requiring comprehensive interventions and therapies that include hospitalization and surgical procedures. The major complications related to anastomosis are anastomotic leakage^{7,8,9,14,10,11,12,13}, anastomotic stricture^{11,12}, anastomotic bleeding⁷, abscess^{7,8,9,14,15}, bowel

obstruction^{16,9,17,18}, sepsis and shock^{9,19}, and ileus^{8,19,14}. Some major complications require blood transfusions¹⁴ and some result in death^{7,16,20,8,9,19}. Additional major complications reported include wound complications, internal hernia, obstructive uropathy, urethral stricture and rectovaginal fistula^{7,12,15}.

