The Safety Population will include all subjects randomized in the study who receive the study treatment, i.e. Colovac or Standard of Care. Subjects will be analyzed according to the treatment actually received. If a subject received Colovac for any duration, the subject will be analyzed in the Colovac treatment group. Otherwise the subject will be included in the Standard of Care group. The Safety Population will be used for all safety-related analyses. This population will be used in the primary safety analysis and missing primary outcome data will not be imputed. All subjects who have the device removed before Day 10 due to a device-related reason will be included in the assessment as failures.

INTENTION TO TREAT POPULATION

All randomized subjects comprise the ITT population and will be tracked. Subjects will be analyzed according to the randomized treatment assignment. This population will be used in the primary efficacy analysis. All subjects who have the device removed and require conversion to ostomy will be included in the assessment as failures. Any missing primary outcome data will be imputed using multiple imputation techniques.

The ITT population will also be used in all other efficacy analyses, without imputation for missing data.

PER PROTOCOL POPULATION

The per-protocol dataset is a subset of subjects who are included in the ITT dataset. Subjects who have major study deviations (i.e., those who do not meet the inclusion/exclusion criteria, those who receive a treatment other than one of the study treatments, or those having other study deviations that could potentially affect clinical outcomes) will be excluded from this dataset. The CEC will determine which study deviations are major.

The per-protocol population will only be used for the analysis of the primary endpoints as a sensitivity analysis.

STATISTICAL METHOD AND ANALYSIS

For general data summary, the number of subjects with data, mean, standard deviation, median, minimum and maximum will be presented for continuous data. Frequency and percentage will be presented for categorical data.

SECONDARY EFFECTIVENESS ANALYSIS

To limit the overall type I error rate to 2-sided 0.05 for the secondary effectiveness endpoints, a gated hierarchical testing approach will be adopted. Four of the secondary effectiveness endpoints will be tested in the order presented below, and as follows:

Cumulative hospital stay post-discharge

Comprehensive Classification Index (CCI)

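### The first test in the secondary hierarchy, cumulative hospital stay, has no rule for subjects who die before 12 months, and its logrank option defines neither event nor censoring

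*Combined protocol and SAP*

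**What the plan says.** - **Place in the plan.** Section 8.6.1 sets a fixed order: "Four of the secondary effectiveness endpoints will be tested in the order presented below". Hospital stay comes first. The next endpoint is tested only if the preceding null hypotheses were "rejected at the 2-sided alpha=0.05 significance level in favor of the Colovac treatment".
- **Quantity.** The endpoint text reads "Total length of hospital stay (in days) through the 12-month visit will be compared between the two study arms". The synopsis has a different time origin: "Cumulative length of hospital stay during the 12 months post-discharge".
- **Test.** Table 10 states the target claim as "The mean cumulative length of hospital stay is significantly less for Colovac subjects through 12 months" than for Control, with a t-test. The endpoint text that follows expects skewed data and names a Wilcoxon rank sum test, or says that "the logrank test (should there be censored data) will be used for analysis". It does not say what the logrank event is or what would count as censored.
- **Missing data.** Section 8.5.2: "The ITT population will also be used in all other efficacy analyses, without imputation for missing data".
- **Death.** None of these places mentions it. Death is counted elsewhere: related Grade V events are major complications in the primary safety endpoint, the CCI (second in the hierarchy) weights all adverse events by severity, and section 8.6.2 asks for a table of adverse events leading to death.

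**The concern.** A subject who dies stops accruing hospital days. A Colovac subject who dies on Day 6 contributes at most 6 days, whereas a survivor in that arm stays until device retrieval at about Day 10. A Control subject who dies after discharge but before stoma reversal never accrues the reversal admission. If accrued days are analysed as they stand, both deaths score as good results.

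With no rule, the statistician must decide after the data are in whether deaths count at accrued days, are censored, are dropped or are ranked worst. These choices can move the result in different directions. The decision falls on the test that opens the hierarchy, so it affects both a possible shorter-stay claim and whether CCI, LARS and EQ-5D-5L are formally tested. A wrong pass matters when Colovac is the arm with more early deaths. If Control has more, the same mechanism works against Colovac.

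**Working it through.** **Nothing to reproduce.** The plan gives no expected difference, SD or power for hospital stay. The check is therefore a simulation under the null hypothesis: the same potential stay in both arms, different mortality. The output is the share of trials significant at two-sided 0.05 in favour of the arm with more deaths. Without distortion it is 2.5%.

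**Inputs from the documents.** 171 per arm; two-sided 0.05; no imputation. The only mortality figure is background: "Overall mortality rates following colorectal surgery range from 1 to 16.4" per cent. That covers colorectal surgery in general and is not a rate expected in this trial.

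**Assumptions.** The stay distributions, mortality pairs and timing of death. In expected deaths per arm, 171 × 0.01 = 1.7, 171 × 0.02 = 3.4, 171 × 0.03 = 5.1 and 171 × 0.05 = 8.6.

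**Simulation A.** Total stay lognormal, median about 13 days, log-SD 0.6; 1,500 trials per row; each death falls at a random point in the subject's potential stay. In the last two columns the first figure favours the arm with more deaths and the second goes against it.

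| Deaths | Wilcoxon, accrued days | t-test, accrued days | Mean difference (days) | Deaths excluded, Wilcoxon | Logrank, deaths censored | Death ranked worst, Wilcoxon |
|---|---|---|---|---|---|---|
| 2% vs 2% | 2.5% | 2.7% | 0.01 | 2.7% | 3.1% / 2.9% | 2.9% / 2.9% |
| 5% vs 2% | 4.3% | 3.0% | -0.16 | 2.0% | 1.5% / 3.7% | 0.6% / 6.0% |
| 10% vs 2% | 10.4% | 8.5% | -0.58 | 3.1% | 1.3% / 5.5% | 0.0% / 23.5% |
| 16.4% vs 1% | 28.0% | 19.7% | -1.11 | 2.9% | 0.5% / 9.1% | 0.0% / 69.7% |

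The Monte Carlo standard error at 2.5% is √(0.025 × 0.975 / 1500) = 0.4 points, so the t-test's 3.0% at 5% vs 2% cannot be told from nominal.

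Two variants on the three unequal rows, Wilcoxon test:
- Deaths among would-be long stayers, cut short: 4.6%, 7.3% and 16.3%.
- Deaths after twice the usual days in hospital: 1.3%, 0.5% and 0.0%. The direction reverses.

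**Simulation B.** Index stay gamma with mean 9 days; a later stay of mean 7 days in 60% of subjects; 3% loss; 3,000 to 4,000 trials per scenario. The gamma shapes are a further assumption, and the ranges below are across repeat runs.

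| Timing of deaths | Mortality | Wilcoxon | t-test |
|---|---|---|---|
| All in the index stay (2-9 days accrued) | 3% vs 1% | 4.4-4.9% | 4.1% |
| Same | 5% vs 2% | 5.5% | 5.2% |
| Same | 5% vs 1% | 6.8-8.0% | 5.8-8.2% |
| Spread over 12 months | 5% vs 1% | 3.2% | 3.4% |
| Spread, plus a terminal admission averaging 7 days | 5% vs 1% | 1.5% | 1.4% |

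Repeat runs at 5% vs 1% gave about 4% for deaths within 90 days and 3.3-3.7% for deaths spread over 12 months. Ranking death worst, with deaths in the index stay, gave 1.0-1.3% at 3% vs 1%, 0.7% at 5% vs 2% and 0.4-0.5% at 5% vs 1%.

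**Reading.** The distortion needs unequal mortality and deaths early enough to shorten the total. Equal mortality produces none. Both simulations give the arms the same underlying stay, whereas the protocol expects different index stays (about 5 days for Control, until retrieval for Colovac). The figures therefore measure distortion under the null, not the result this trial would show.

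**The case against.** A reader might infer that the plan credits death as a benefit, so that excess mortality makes an arm look better, and that the logrank clause is the proof. The documents do not support that. They choose no rule for death; they are silent. Nor does the logrank clause point that way. With deaths censored at accrued days, the arm with more deaths was favoured in 1.5%, 1.3% and 0.5% of trials, below nominal. Coding death as the end of stay would bring the short-stay effect back, but the plan does not say which coding applies.

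Four further objections have weight:
- **Size.** The figures near 8% require every death to fall in the index stay at 5% vs 1%. This holds, and is why the result is given as a range by timing.
- **Plausibility.** The eligibility criteria remove many high-risk patients, and under Table 8 a single death at least possibly related to the device halts implantation pending DSMB review. A large device-driven excess could hardly build up unnoticed. This makes the upper rows of Simulation A remote, but it does not define the analysis.
- **Other safeguards.** Study success needs non-inferiority on primary safety, which counts related deaths, so a false pass on hospital stay cannot deliver it. However, primary safety gives a related death the same weight as any other major complication, and CCI is tested only after hospital stay has been won. Neither corrects the hospital-stay claim.
- **No imputation.** Barring imputation is not itself the fault. If accrued days are used, nothing is missing. If deaths are dropped and are unrelated to potential stay, the error rate is about nominal (2.0-3.1%).

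The reversal after long terminal stays defeats any claim of a fixed direction. It also shows why a rule is needed in advance.

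**Conclusion.** The omission is real. The endpoint that opens the secondary hierarchy has no rule for death before 12 months. Its plain reading scores an early death as a short stay under the Wilcoxon or t-test, and the logrank alternative is undefined and would, if deaths were censored, treat them as uninformative.

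At assumed mortality of 3-5% vs 1-2%, the false shorter-stay rate for the arm with more deaths is about 4-8% if deaths fall in the index stay, about 2.5-3.7% if spread over 12 months, and below 2.5% after long terminal admissions. These rates rest on assumed stay distributions and mortality; the documents give no trial-specific figure for either.

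Severity is low to moderate. The primary conclusion is not at risk. A secondary claim, and access to the three tests behind it, would rest on an analysis decision that is still open.

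**What to change.** Amend the SAP before any unblinded comparison:
1. Name one rank-based test for hospital stay, replacing the t-test in Table 10, and delete the logrank option. Worst rank cannot be applied to a t-test on means, so this conflict has to be settled first.
2. Either rank death before 12 months as the worst outcome, or redefine the endpoint as days alive and out of hospital to Day 365. Choose one now.
3. Fix one time origin. The post-discharge wording and the wording through the 12-month visit differ, and a subject who dies in the index stay has no post-discharge period.
4. Say separately how totals cut short by withdrawal or loss to follow-up are handled.
5. Show deaths by arm beside the hospital-stay result; section 8.6.2 already plans a table of adverse events leading to death.

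The cost is SAP wording. Admission dates are needed for the endpoint anyway, and deaths are already reported to the sponsor. The downside is small: the endpoint is no longer pure hospital days, and the Table 10 claim about means must be reworded.
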